8. PARTICIPANT & PATIENT IDENTIFICATION

8.1. Consultants, Fellows, and Specialty Registrars

Group 1 ('StR's'): Trauma & Orthopaedic Specialty Registrars on Arthroplasty clinical placements.

Group 2 ('Experts' and 'Fellows'): Consultant Orthopaedic Surgeons, and nationally appointed Orthopaedic Arthroplasty Fellows.

Inclusion Criteria

Group 1 ('StR's'): All Specialty Registrars holding a National Training Numbers (NTN) in Trauma & Orthopaedic Surgery within the Thames Valley (Oxford) Deanery and who are or will be working on arthroplasty clinical placements at either the NOC, Oxford University Hospitals NHS Foundation Trust, or WGH, Buckinghamshire Healthcare NHS Trust over the specified recruitment period will be eligible for participation in this study. We anticipate recruiting 2 StR's from each recruitment centre every 6 months, over an 18 to 24-month period (total n = 12-16).

Group 2 ('Experts' and 'Fellows'): All Consultant Orthopaedic Surgeons with a sub-specialty practise in adult reconstructive (arthroplasty) surgery holding substantive posts at the NOC are eligible for participation in this study. The Consultant Orthopaedic Surgeons at WGH will not be required for the intra-operative assessment within this study, as we will gather sufficient motion data from the NOC Consultants to be able to benchmark an 'expert' performance. Nationally appointed Orthopaedic AF's working at either at either the NOC, Oxford University Hospitals NHS Foundation Trust, or WGH, Buckinghamshire Healthcare NHS Trust over the specified recruitment period will be eligible for participation in this study. We anticipate recruiting 2 AF's every 6-months over an 18 to 24-month period (total n = 6-8)

Exclusion Criteria

- Inability to comply with study procedures or timetable

- Moving outside of the area, relinquishing their position, or National Training Number.

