9. PROTOCOL PROCEDURES

9.1. Recruitment

9.1.1 Consultant, Fellow and Specialty Registrar recruitment

Group 1: Specialty Registrars ('StR's').

StR's will be identified within the Oxford Deanery's T&O Higher Surgical Training Programme. The current Training Programme Director (TPD), [name] (Consultant Orthopaedic Surgeon at Milton Keynes University Hospital) has overall responsibility for allocating clinical placements to StR's. With the agreement and assistance of the TPD, we will identify the StR's who have been allocated clinical placements within the named recruitment centres over the upcoming 18 to 24-month recruitment period starting from September 2019, and contact them directly via e-mail to ask if they would be interested in participating in this study. There is a regional T&O StR group e-mail list, which will be used to inform all StR's of this study. Furthermore, the lead researcher will attend the weekly T&O StR Teaching Programme in advance of the start of this study to hand out PIS in person, and any questions can be directly addressed.

Group 2: Consultant Orthopaedic Surgeons ('Experts'), and nationally appointed Orthopaedic Arthroplasty Fellows ('Fellows').

The Experts and Fellows at the NOC and WGH will be approached in person to ask if they would be interested in participating in this study. A PIS outlining the study, including their role, will be provided for their attention, and any questions can be directly addressed.

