9.4 Randomisation

Randomisation will be performed via a blinded sealed envelope containing information regarding which arm of the study they will participate in. As we only anticipate recruiting 2 StR's from each recruitment centre every 6 months, a more complex allocation/randomisation procedure will not be required. Over the 18 to 24-month study period we aim to recruit and randomise 6-8 StR's to the 'intervention' group, and randomise 6-8 StR's to the 'control' (routine training) group, with an even distribution of these StR's in both groups across the two recruiting hospital sites.

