11 STATISTICS AND ANALYSIS

Analysis of motion data.

Motion data from the wireless sensors produces performance surrogate markers such as: the number of movements (major & minor); total path length; and smoothness/economy of movement. Data distributions will be assessed for normality using the Shapiro-Wilk test. Previous studies show such data are not normally distributed, and we would expect to use non-parametric tests, such as the Mann-Whitney U test to compare the performance metrics between the 2 groups of participants (StR's against Experts & Fellows). The Mann-Whitney U test will also be used to compare performance metrics between the two sub-groups of StR's (control and intervention), and also within the intervention sub-group in order to compare performance before and after training.

Performance metrics within all groups of participants will be reported using descriptive statistics to outline the central tendency (mean, median, and mode) and variation (range, variance, and standard deviation) in readings obtained. The Kruskal-Wallis one-way analysis of variance (ANOVA) test will be used to test for differences in the mean values obtained for all performance metrics between the two groups of participants. The Wilcoxon signed-rank test will be used to determine any differences in performance metric between the two groups.

Analysis of other routinely obtained data

X-ray (radiograph) analysis:

X-rays will be reviewed by two independent Consultant Orthopaedic Surgeons who will be blinded to the patient and lead surgeon's identity in order to reduce bias. There are several important parameters to be evaluated when reviewing a pelvic x-ray, therefore we will ask each reviewer to allocate a categorical global rating (see below) for both the pre- and post-operative x-rays. [5] The Chi-squared test will be used

to determine if there are any significant differences between each group, and also intra-group differences (for example StR's before and after additional training).

Pre-operative x-ray

- 1: Hip osteoarthritis without significant bone loss.
- 2a: Hip osteoarthritis with significant bone loss on acetabular side.
- 2b: Hip osteoarthritis with significant bone loss on femoral side.
- 3: Hip osteoarthritis with significant bone loss on both acetabular and femoral sides.

Post-operative x-ray

- 1: Excellent implant position and restoration of hip anatomy.
- 2a): Good overall with minor imperfections on acetabular side.

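### The planned comparison of registrars with Experts & Fellows ignores hospital, although half the registrars and no Consultants are at WGH and the Fellows' split is unstated

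*Combined protocol and SAP*

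**What the plan says.** - **Consultants.** Section 8.1 admits those "holding substantive posts at the NOC are eligible for participation in this study". It adds that "The Consultant Orthopaedic Surgeons at WGH will not be required for the intra-operative assessment within this study", and gives the reason: "as we will gather sufficient motion data from the NOC Consultants to be able to benchmark an 'expert' performance".
- **Registrars.** Section 8.1 states "We anticipate recruiting 2 StR's from each recruitment centre every 6 months". Section 9.4 plans the randomised arms "with an even distribution of these StR's in both groups across the two recruiting hospital sites".
- **Fellows.** Section 8.1 accepts "Nationally appointed Orthopaedic AF's working at either at either the NOC, Oxford University Hospitals NHS Foundation Trust, or WGH". It does not say how many are expected at each hospital.
- **Analysis.** For motion data, section 11 uses the Mann-Whitney U test to "compare the performance metrics between the 2 groups of participants (StR's against Experts & Fellows"). For theatre time, haemoglobin, length of stay and PROMs it uses an unpaired t-test or Mann-Whitney U test between groups. For transfusion and morbidity it uses a Chi-squared or Fisher's exact test. Hospital appears in none of these, either as a stratum or as a covariate.
- **Care.** Section 7 leaves the operation, peri-operative care and follow-up to routine practice at each hospital.
- **Recruitment.** Section 9.1.1 says "The Experts and Fellows at the NOC and WGH will be approached in person". This does not sit easily with the eligibility text in section 8.1.

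**The concern.** The two hospitals belong to different NHS Trusts. Where care is left to local routine, length of stay, transfusion, haemoglobin change and theatre time may reflect the hospital as well as the surgeon. If the trainee and expert groups are spread differently over the hospitals, part of any difference between the Trusts will appear as a difference in experience, or will mask one. Section 9.4 shows that the authors wanted hospital balanced between the randomised arms. The trainee-versus-expert comparison has no such protection, and it bears on the secondary objective about surgical experience. The stated reason for using NOC Consultants alone concerns whether there are enough motion data for a benchmark. It does not address whether their patients are a fair comparator for patients operated on by registrars at WGH.

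**Working it through.** **Inputs (synopsis and section 8.1).** 16 StRs with 8 operations each, 8 Fellows with 5 each, 5 Consultants with 5 each.

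**Plan's own figure.** 16 × 8 + 8 × 5 + 5 × 5 = 128 + 40 + 25 = 193, which matches the synopsis. This is a count; the documents give no power calculation to reproduce.

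**Share of operations at WGH.**
- StRs: equal recruitment per centre puts 8 of 16 at WGH, so 64/128 = 50%.
- Consultants: 0/25 = 0%.
- Pooled Experts & Fellows, with F of the 8 Fellows at WGH: 5F/65. Counted by surgeon, the share is the same: F/13.

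**Bias.** Let D be the WGH-minus-NOC difference on an outcome for reasons unrelated to the surgeon. With no experience effect, the expected StR-minus-comparator difference is

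D × (WGH share of StRs − WGH share of comparator).

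| Comparator | WGH share | Bias |
|---|---|---|
| Consultants only | 0/25 = 0% | +0.50D |
| Pooled, F = 0 | 0/65 = 0% | +0.50D |
| Pooled, F = 4 | 20/65 = 30.8% | +0.19D |
| Pooled, F = 6 | 30/65 = 46.2% | +0.04D |
| Pooled, F = 8 | 40/65 = 61.5% | -0.12D |

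Exact balance needs 5F/65 = 0.5, so F = 6.5. If, purely as an assumption, usual length of stay differed by 1 day, the spurious pooled difference would lie between +0.50 and -0.12 day.

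**Lower end of planned recruitment.** With 12 StRs and 6 Fellows, Group 2 has 6 × 5 + 25 = 55 operations. With 0, 3 or 6 Fellows at WGH the shares are 0%, 15/55 = 27.3% and 30/55 = 54.5%, giving biases of +0.50D, +0.23D and -0.05D. The picture is the same.

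**Illustrative false-positive rates.** These come from a simulated Mann-Whitney U test (two-sided 0.05, 4,000 runs) with no experience effect and independent normal data at operation level. The hospital effects are assumed.

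| Comparator | 0.3 SD | 0.5 SD | 0.8 SD |
|---|---|---|---|
| Consultants only | 10% | 20% | 40% |
| Pooled, F = 0 | 16% | 35% | 68% |
| Pooled, F = 4 | 6% | 9% | 13% |
| Pooled, F = 8 | 5% | 6% | 7% |

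These rates ignore clustering by surgeon. With one value per surgeon the inflation is much smaller: the highest rate is 14%, at 0.8 SD with F = 0.

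**After stratification.** In the same operation-level setting, a van Elteren test stratified by hospital (3,000 runs) gives 4.6% to 6.0% for assumed effects of 0.5 and 0.8 SD with F = 0, 4 or 8.

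**The case against.** The strongest reply is that section 11 plans a pooled comparison, and no StR versus Consultant test is specified. The lay summary offers only a possible Consultant-versus-Fellow sub-group analysis. Fellows supply 40 of the 65 Group 2 operations and may be at either hospital, so the imbalance could be close to nil. This stands: a reader might infer from the NOC-only Consultants that the planned comparison is biased by half the hospital difference, but that holds only if no Fellow is at WGH.

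Second, D is not in the documents. Some sources of variation are limited: eligibility is restricted to primary osteoarthritis without complex pathology or previous surgery on that hip, one data-collection protocol applies, and the two x-ray graders are blinded to patient and lead surgeon. This also stands, and it weakens the concern for motion metrics. It does not remove differences in discharge, transfusion or theatre practice.

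Third, a reader might infer that the expert standard itself is undermined. It is not: the benchmark is a description of Group 2's own data and does not rest on a test against StRs. Nor does section 11 contain an analysis relating metrics to outcomes, so there is none to stratify.

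Fourth, sections 8.1 and 9.1.1 may be compatible. Section 8.1 excuses WGH Consultants from the intra-operative assessment, and WGH Consultants could be approached as supervisors. That is possible, but section 9.1.1 speaks of Experts participating, so the text needs clarifying.

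**Conclusion.** The concern holds in a limited form. The non-randomised comparison of StRs with pooled Experts & Fellows can confuse experience with hospital, mainly for care-pathway outcomes. Its bias runs from +0.50D to -0.12D depending on a Fellow split that the protocol does not state, so neither size nor direction is known in advance. Any StR versus Consultant contrast that is reported would carry 0.50D. These multiples rest on planned numbers and equal StR recruitment per hospital; D and the SD-based error rates are assumptions.

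A reader might extend the point to the primary, randomised StR comparison. The documents do not support that, because the arms are meant to be evenly spread over the hospitals. This is an inexpensive improvement to a secondary comparison and does not threaten the trial's main question.

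**What to change.** In section 11:

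1. Stratify every StR versus Experts & Fellows comparison by hospital, for example with a van Elteren test for continuous outcomes and a Mantel-Haenszel or exact stratified test for binary outcomes.
2. Report how many Fellows, and how many of their operations, were at each hospital.
3. Limit any StR versus Consultant claim about patient outcomes to NOC operations: about 64 StR against 25 Consultant operations, or 8 against 5 surgeons.

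Add hospital to the data items in section 12, which does not list it; section 12.6 already has patient data taken from each recruiting Trust's system. Reconcile section 9.1.1 with section 8.1 on which Consultants are approached and for what role, since the answer changes the imbalance.

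No new patients, procedures or sites are needed. The cost is lower precision. If no Fellow works at WGH, the 64 StR operations there contribute nothing to this comparison, and stratifying cannot supply a Consultant contrast at a hospital where no Consultant is assessed. Nor does stratifying by hospital deal with repeated operations by the same surgeon, which is a separate matter.

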8.2. Patients

Adult patients (aged 18 years or above) diagnosed with primary hip osteoarthritis who have been listed for elective primary THR in the NHS.

Inclusion Criteria

- Adult patients (aged 18 years or above) diagnosed with primary hip osteoarthritis who have been listed for elective primary THR in the NHS.
- THR operation performed by a surgeon participant as lead surgeon.

Exclusion Criteria

Patients may not enter the study if ANY of the following apply:

- Patients with complex hip pathology (e.g. previous trauma, hip dysplasia, infection).
- Patients who have had previous surgery on their affected hip.

9. PROTOCOL PROCEDURES

9.1. Recruitment

9.1.1 Consultant, Fellow and Specialty Registrar recruitment

Group 1: Specialty Registrars ('StR's').

StR's will be identified within the Oxford Deanery's T&O Higher Surgical Training Programme. The current Training Programme Director (TPD), [name] (Consultant Orthopaedic Surgeon at Milton Keynes University Hospital) has overall responsibility for allocating clinical placements to StR's. With the agreement and assistance of the TPD, we will identify the StR's who have been allocated clinical placements within the named recruitment centres over the upcoming 18 to 24-month recruitment period starting from September 2019, and contact them directly via e-mail to ask if they would be interested in participating in this study. There is a regional T&O StR group e-mail list, which will be used to inform all StR's of this study. Furthermore, the lead researcher will attend the weekly T&O StR Teaching Programme in advance of the start of this study to hand out PIS in person, and any questions can be directly addressed.

Group 2: Consultant Orthopaedic Surgeons ('Experts'), and nationally appointed Orthopaedic Arthroplasty Fellows ('Fellows').

The Experts and Fellows at the NOC and WGH will be approached in person to ask if they would be interested in participating in this study. A PIS outlining the study, including their role, will be provided for their attention, and any questions can be directly addressed.

9.1.2 Patient Recruitment

Following screening and identification of patients using waiting lists within the Orthopaedic Department at the 2 named NHS Hospitals, the PI ([name]), or a suitably qualified deputy, will attend the patient's routine

POAC appointment in order to highlight with the direct clinical care team that the patient may be eligible for participation in this study. The patients direct clinical care team will then approach the patient to enquire about participation in this study, and only if interest to participate is expressed, they will then be referred onto the PI. The PI will then proceed to confirm eligibility, and outline the purpose of the study. A patient information sheet and verbal information will be provided on: what data we will be collecting and specifically how it will be used; and any risks and benefits to taking part.

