The outcome measures will be surgeon-specific and patient-specific. These outcome measures for the 'Trainee' group will commence following completion of the simulation training (if applicable), whereas they can commence immediately following study approval for the 'Expert' group. The surgeon-specific outcome measures will be the objective motion-analysis metrics generated by validated and extensively used wireless sensors placed on the elbows of surgeons under their sterile gowns during the operation; and subjective assessments of surgical trainee performance using validated and reliable forms of structured human grading. Patient-specific outcome measures will be collected for a pre-determined number of patients who have undergone a primary elective THR by any of the surgeon participants in this study. All patient-specific outcome measures (with the exception of a post-operative questionnaire) are routinely collected as part of the patients NHS clinical care, and no other additional investigations are required for conducting this research. All patients will be asked to provide their written informed consent for the use of their data in this study. The patient-specific outcome measures include: pre- and post-operative blood tests and radiograph (X-ray) analysis; the incidence of blood transfusions and any other peri-operative complications; the in-patient length of stay; and two patient-reported outcome measure (PROMs) questionnaires.

Statistical analysis will then be performed on the data collected, specifically aiming to identify any significant differences in either surgeon performance metrics, or patient outcome measures between:

- 1) The StR's who have undertaken additional simulation training versus those who have routine Deanery training.
- 2) The 'Trainee' group and the 'Expert' group. A sub-group analysis may be performed within the 'Expert' group also to determine any differences between the Consultants and Fellows.

In summary, this novel research will use validated methodology and routinely collected patient outcome measures in order to determine the impact of simulation training on surgical trainee performance and patient outcomes following a primary elective THR, and also help to benchmark an expert level of performance in this commonly performed and highly effective operation. The results of this study will hopefully help in shaping the future of orthopaedic surgical training and assessment within the United Kingdom.

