7. STUDY DESIGN

Please see Appendix A for study flow diagram.

This is a prospective randomised controlled study designed to assess the impact of specific training interventions on surgical trainee's operative performance and patient outcomes following primary elective THR. We will also study the performance and patient outcomes of both 'Experts' and 'Fellows' in an additional comparator group, which will allow a potential expert standard in THR to be defined.

All study participants will be recruited from 2 Hospitals within the Thames Valley (Oxford) Post-graduate Medical Deanery, and will be composed of: Trauma & Orthopaedic Specialty Registrars ('StRs') holding national training numbers; Consultant Orthopaedic Surgeons ('Experts'); and Orthopaedic Arthroplasty Fellows ('Fellows'). Over the 18-24 month anticipated study period we aim on recruiting a total of up to 16 StR's, 8 Fellows, and 5 Experts. See section 9 for further details on participant recruitment.

StR's will be randomised in a 1:1 ratio to receive either: routine normal Deanery training (the control group, n=8); or routine normal Deanery training with additional simulation-based and cognitive learning (the intervention group, n=8). The intervention group will receive this training for 1-2 hours per week over a 4 to 6-week period. The 'Experts' and 'Fellows' will not be eligible for any intervention, and will act as a separate comparator group.

All participants will be assessed intra-operatively at set timepoints when performing elective primary THR surgery on patients within the named NHS Hospitals. The timepoints will vary depending upon each group. Each StR enrolled into this study will be assessed at a minimum of 8 separate THR operations over a 6-month period, commencing at 6 weeks in to their 6-month clinical placement. Both the 'Fellows' and 'Experts' will be assessed at a minimum of 5 separate THR operations depending upon the reliability of their performance data.

All patients in this study will have been listed for routine elective primary THR surgery under a named Orthopaedic Consultant on the NHS. There will be no interventions or deviations from routine clinical practise regarding the pre-operative investigations or work-up, the operation itself, the peri-operative care, or post-discharge follow-up.

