9.2. Informed Consent

The PI ([name]), or a suitably qualified deputy, will take informed consent from every participant involved in this study. This will be taken at their visit before any study specific procedures are performed.

Each participant must personally sign and date the latest approved version of the Informed Consent form at this visit. Written and verbal versions of the PIS and Informed Consent form (ICF) will be presented to the participants detailing no less than: the exact nature of the study; what it will involve for the participant; the implications and constraints of the protocol; and any risks involved in taking part. It will be clearly stated that the participant is free to withdraw from the study at any time for any reason, and with no obligation to give the reason for withdrawal. The participant will be allowed as much time as wished to consider the information, and the opportunity to question the Investigator, or other independent parties in order to decide whether they will participate in the study. Written Informed Consent will then be obtained by means of participant dated signature and dated signature of the person who presented and obtained the Informed Consent. A copy of the signed Informed Consent will be offered to the participant. The original signed form will be retained by the PI ([name]) at the study site

Visit 1 - Group 1 ('StR's):

Following enrolment for participation in this study, the StR's will be randomly allocated to receive either routine normal Deanery training (the 'control' group), or routine normal Deanery training plus additional simulation training (the 'intervention' group). Following randomisation all StR participants will undergo a baseline written and practical skills assessment within the OOSEC.

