9.5 Blinding and code-breaking

Standard surgical practise will be followed. Patients are not formally blinded to which Surgeon (Consultant, Fellow, or StR) performs their operation, and are informed if requested. In line with standard surgical practise and training within the NHS, patients will provide informed consent that they understand no guarantees can be given that a particular person will perform the procedure. The person will, however, have appropriate experience.

Due to the nature of this study the StR's cannot be blinded to their allocations into either the 'control' or 'intervention' groups, however the assessment methods and any assessors will be blinded.

9.6 Description of study intervention(s),

The intervention to be tested is the simulation-based and cognitive learning package, which will be delivered to a randomised sub-group of 50% of the StR's recruited into this study. This will be delivered in a supervised setting within the OOSEC over a 4-week period for between 1 to 2 hours per week, over 3 to 4 consecutive but separate six-month placements (please see Appendix A for Study Flow Diagram). This will take place on a Wednesday afternoon, which is when all the Regional StR's are due to attend teaching in Oxford at the NOC.

The OOSEC is a secure enclosed laboratory space within the NOC, which contains all the necessary equipment required to run the simulation-based and cognitive learning training. The simulation training in general may include:

- 1) Focussed workshops on saw-bone models (simulated bones)
- 2) Digital and computer-based cognitive learning packages
- 3) Virtual reality platforms.

All participants within group 1 (StR's) will be asked to attend and complete baseline and final assessments within the OOSEC, which will consist of a multiple-choice questionnaire (MCQ) and a simulated procedure. Participants within group 2 (Consultants and Fellows) will only be required to complete a baseline simulated procedure.

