9.7 Intra-operative surgeon performance data collection

The following protocol will apply to all episodes of intra-operative performance data collection for StR's and Fellows. The intra-operative data collection for Consultant performed operations will differ slightly in that they require no supervision, and no surgeon will 'take over' the operation. However, the methods for recording the intra-operative data will remain the same.

A maximum of two study participants (excluding Consultants) will attend any given list. The PI ([name]) will attend the World Health Organisation (WHO) briefing in theatre on the morning of the list, introduce themselves and explain their role during the list. If recording an StR, neither the participant or PI will disclose which arm of the study the participants are in (routine training, or additional simulation training). The supervising Consultant will confirm the cases on the list the StR or AF's will be performing under supervision and training.

Operative protocol

After anaesthesia and patient set-up, the supervising Consultant and participant will scrub in up in the usual manner with the motion sensors in position on the lead surgeon's elbows under their sterile gown (see Appendix C). The procedure will then continue routinely and normally, but with the PI collecting motion data via the wireless Bluetooth sensors. The PI will also manually record the timings of each stage of the THR operation. This process will allow synchronisation of motion data to the participants progression throughout the stages of the operation. Data collection will stop when the dressing has been applied to the surgical wound.

Following completion of the operation, the participants in conjunction with the supervising Consultant will be asked to complete short written assessments of the lead surgeons' intra-operative performance. These assessments may include: Global Rating Scales (GRS), Objective Structured Assessment of Technical Skills (OSATS), and surgical checklists.

Intra-operative deviations or interruptions

Sometimes the supervising Consultant needs to take over part or all of an operation if it proves particularly difficult. In the event that a procedure has to be taken over completely by the Consultant then data recording will stop. If minor adjustments only are made by the Consultant during the operation then these will be noted and time marked against the motion data.

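### Patients are selected after the registrars are randomised, with no blinded eligibility decision, an open-ended exclusion and no case-mix adjustment, so the hips could differ by arm

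*Combined protocol and SAP*

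**What the plan says.** **Order of events.** StRs are randomised at Visit 1 (section 9.2): "Following randomisation all StR participants will undergo a baseline written and practical skills assessment within the OOSEC". The lay summary (section 2) adds: "These outcome measures for the 'Trainee' group will commence following completion of the simulation training (if applicable". Section 7 has their operative assessments "commencing at 6 weeks in to their 6-month clinical placement".

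**Who decides eligibility.** Under 9.1.2 the PI or a qualified deputy goes to the pre-operative assessment clinic (POAC) after the waiting lists have been screened. The direct care team approaches the patient, and then "The PI will then proceed to confirm eligibility, and outline the purpose of the study". Under 9.2 the PI or a deputy also takes consent.

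**Who is blinded.** Section 9.5 accepts that StRs know their arm, "however the assessment methods and any assessors will be blinded". It does not mention the person deciding eligibility. Section 9.7 says that on the morning of a list "neither the participant or PI will disclose which arm of the study the participants are in".

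**The criteria.** Section 8.2 requires primary hip osteoarthritis and an operation led by a surgeon participant. It excludes previous surgery on that hip and, as an open list, "Patients with complex hip pathology (e.g. previous trauma, hip dysplasia, infection" and the like. Section 11 grades pre-operative films up to "3: Hip osteoarthritis with significant bone loss on both acetabular and femoral sides".

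**Later steps.** The supervising Consultant confirms the StR's cases at the theatre briefing (9.7). The Investigator may discontinue a patient whose ineligibility is found retrospectively (9.8). Section 11 lists unadjusted tests only.

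**The concern.** The randomised unit is the surgeon. Randomising up to 16 StRs balances the StRs on average, but it protects the comparability of their patients only if patients enter without regard to arm. Here StR patients contribute data after the arms exist. The PI's eligibility decision is not described as blinded, and one exclusion leaves room for judgement.

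If harder hips enter one arm less often, knowingly or not, then operating time, path length, blood loss and X-ray grade could differ with no training effect. Recruiting more patients would not remove such a difference, and none of the planned tests would correct for it.

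**Working it through.** **1. The plan's own figure.** Section 3 gives 193 patients: 16×8 + 8×5 + 5×5 = 128 + 40 + 25 = 193, which reproduces. The StR comparison therefore has 8×8 = 64 patients per arm. No alpha, power, effect size, SD or intra-class correlation (ICC) is given, so everything from step 4 on is illustration.

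**2. Where could arm influence entry?**

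| Step | Section | Is the arm tied to the patient? |
|---|---|---|
| Screening and eligibility at POAC | 9.1.2 | Not formally; the operating surgeon is not guaranteed (9.5) |
| Choice of the StR's cases | 9.7 | Yes, from this point; the Consultant is meant not to be told the arm |
| Led by a surgeon participant | 8.2 | Yes; can be met only at surgery |
| Retrospective ineligibility | 9.8 | Yes; the operation may already be done |

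**3. How often is the arm predictable at POAC?** Section 9.4 expects 2 StRs per site every 6 months. If both are in the same arm, the PI knows the arm of any StR patient there, whichever StR operates. The chance of this is:
- simple randomisation: 1/2 = 50%;
- 8:8 overall: 7/15 = 47%;
- 4:4 within each site: 3/7 = 43%;
- each pair split between arms: 0%, but the plan states no such rule.

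A list known in advance to be a particular StR's would also make the arm predictable. The documents do not say how often that happens.

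**4. Size if harder hips are screened out of one arm (assumed inputs).** Let a share p of candidate hips be harder, and remove a fraction r of these from one arm only. That arm's harder share becomes p(1−r)/(1−pr).
- p = 0.20, r = 0.5: 0.10/0.90 = 0.111, a difference of 0.089.
- p = 0.30, r = 0.5: 0.15/0.85 = 0.176, a difference of 0.124.
- r = 1: differences of 0.20 and 0.30.

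If a harder hip is 1 SD worse, these are the biases in SD units.

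**5. Limiting this to predictable blocks.** If POAC exclusion acts selectively only where both StRs share an arm, about 43-50% of that arm's StRs are affected. For r = 0.5 the bias is 0.43×0.089 = 0.04 to 0.50×0.124 = 0.06 SD. For r = 1 it is 0.43×0.20 = 0.09 to 0.50×0.30 = 0.15 SD.

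**6. Effect on the false-positive rate (two-sided 5%, assumed).** With n = 64/(1+7×ICC) effective patients per arm and z = bias/√(2/n), the rate is Φ(z−1.96) + Φ(−z−1.96). Example: bias 0.30, ICC 0 gives √(2/64) = 0.177, z = 1.70 and a rate of 39.6%.

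| ICC | n | Bias 0.05 SD | Bias 0.10 SD | Bias 0.30 SD |
|---|---|---|---|---|
| 0 | 64 | 5.9% | 8.7% | 39.6% |
| 0.05 | 47.4 | 5.7% | 7.8% | 30.9% |
| 0.2 | 26.7 | 5.4% | 6.5% | 19.5% |

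These rates assume a standard error corrected for clustering by surgeon.

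**The case against.** **The decision point is wrong.** A POAC exclusion mostly removes a hip from a pool shared by both arms and by the Fellows and Consultants. Nothing pairs an StR with a Consultant, so listing under a named Consultant does not reveal the StR. This largely stands. It confines the POAC route to settings where the arm is predictable, but it does not touch case choice or retrospective removal.

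**The PI's knowledge is inferred.** This is correct. A promise not to disclose makes sense only if the PI knows the arm, but no section says so outright. Nor is the POAC visit dated relative to Visit 1, and the flow chart is not available.

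**The exclusion is clearer than alleged.** Its examples are pathologies other than primary osteoarthritis, whereas the bone-loss grades are all labelled as osteoarthritis. The natural reading is that such hips are eligible. A reader might infer that a screener could just as well call them complex; the text does not support going that far. The list is nevertheless open, and 8.2 is silent on the grades.

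**Case mix is already measured.** Two Consultants blinded to patient and lead surgeon grade the pre-operative films, groups are compared by Chi-squared test (section 11), and age, gender and BMI are collected (section 12). This is a real safeguard. It can show imbalance among enrolled patients, but not who was left out, and no analysis uses it for adjustment.

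**Outcomes are collected for every patient of a participating lead surgeon (section 6).** That governs data collection within the study. It does not say that every eligible patient is invited.

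**The bias is small against the noise.** At 0.09-0.12 SD it is below one standard error (0.177 SD before clustering). This is true, but it would still move the estimate.

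**Conclusion.** The concern holds as a risk built into the design. StR allocation precedes their patients' data, the eligibility decision is not described as blinded, the exclusion is open-ended, retrospective removal is allowed, and neither consecutive invitation nor case-mix adjustment is planned.

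A reader might infer that the PI can steer difficult hips away from one arm at the clinic, or that the arms will in fact differ. The documents support neither. The surgeon is not fixed at that stage, and selective exclusion there needs a predictable arm. Case choice and retrospective removal are the routes more directly tied to arm.

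The size is entirely assumed. Biases of 0.05-0.30 SD correspond to false-positive rates of about 5% to 40%, depending on ICC. The upper end requires every harder hip to be kept out of one arm and none out of the other. Restricting the POAC route to same-arm pairs, with half of the harder hips excluded, gives 0.04-0.06 SD. The change is worth making because it is cheap, not because a large bias has been shown.

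**What to change.** - **9.1.2:** have clinical eligibility confirmed and fixed before surgery by a member of the direct care team who is not a study StR and is kept unaware of StR allocation. The protocol must state this unawareness, as no section now does. Invite consecutive eligible patients.
- **8.2:** replace the open list with a closed one, and state whether pre-operative grades 2a, 2b and 3 are eligible.
- **9.8:** decide any retrospective ineligibility without knowledge of arm and from pre-operative information only.
- **Log:** record screened, excluded and declined patients by site and 6-month block, since patients never assigned to an StR cannot be logged by StR. For enrolled patients, record case assignment, takeover and removal by StR and arm. The log makes selection in the Consultant's case choice visible; it does not prevent it.
- **Section 11:** report the already graded pre-operative X-rays by arm, and adjust the StR arm comparison for grade, age and BMI.

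The cost is protocol wording, a log and a little extra form-filling for the care team. The clinic visit, the blinded grading and the demographic data are already in the plan.
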